5.2 Withdrawal of subjects from study²¹

5.2.1 Withdrawal²² - amended

Subjects *must* be withdrawn from the study for the following reasons:

- At their own request or at the request of their legally acceptable representative
- At any time during the study and without giving reasons, a subject may decline to participate further. The subject will not suffer any disadvantage as a result.
- If, in the investigator's opinion, continuation of the study would be harmful to the subject's well-being

Subjects may be terminated from the study by the Investigator. Reasons for termination of a subject from the study may include, but are not limited to, the following:

- Subject does not retain device (e.g. due to removal of device, expulsion, salpingectomy or other utero-tubal surgeries)

¹⁹ Per Amendment 4 and 5

²⁰ Per Amendment 4

²¹ New section from sponsor template per Amendment 4

²² Withdrawal criteria adapted to suit a device meant for permanent wearing per Amendment 6.

- Death
- An adverse event (AE) preventing study participation
- Lost to follow-up and inability to contact the subject. Note that if a subject who is lost to follow-up is re-contacted, the subject will not be considered to have withdrawn from the study.

A subject who discontinues study participation prematurely for any reason is defined as a “dropout” if the subject has already undergone the NovaSure procedure.

A subject who, for any reason (e.g. failure to satisfy the selection criteria), terminates the study before the time point used for the definition of “dropout” (see above) is regarded a “screening failure”.

Any subject removed from the trial will remain under medical supervision until discharge or transfer is medically acceptable.

In all cases, the reason for withdrawal must be recorded in the case report form (CRF) and in the subject's medical records.

Details for the premature termination of the study as a whole (or components thereof [e.g. centers, treatment arms, dose steps]) are provided in Section 10 (Premature termination of the study).

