7.1.2.5 Notification of Other Relevant Events

The subject should be instructed at the beginning of the study to inform the site immediately if subject has had or is scheduled to have any surgery which may remove some or all of her reproductive organs (i.e. hysterectomy, salpingectomy or oophorectomy)²⁹.

The subject will also be instructed to contact the Investigator immediately if, at any time during the study, subject thinks she might be pregnant.

If a subject experiences a micro-insert expulsion or removal during or following the NovaSure procedure, subject will be followed for the duration of the adverse event, then terminated from the study.

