3.1 Primary Endpoint

- Occurrence of confirmed pregnancy at 1 year and 3 years among subjects relying on Essure micro-inserts for permanent birth control when NovaSure is performed following a successful Essure Confirmation Test.

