6.2 Efficacy

6.2.1 Primary Efficacy Analysis

The primary effectiveness endpoint of this study is the 1-year and 3-year pregnancy rates. The rates will be calculated as done in prior Essure studies, as described below.

Each woman-month of follow-up represents a “Bernoulli trial” of the Essure device. A woman contributes as many women-months as her participation in the post-approval study. Upon observing f failures (pregnancies) in w women-months, the posterior distribution of the monthly failure rate, r , is calculated as:

$$r = \text{beta}(a+f, b+w-f)$$

where a and $b = 0.5$, representing a non-informative prior distribution. The upper Bayesian credible interval of r is easily calculated from the inverse beta function. A 1-year failure rate can be calculated as:

$$1\text{-year rate} = 1 - (1 - r)^{12}$$

The 1-year rate will be calculated when all participating women have reached at least 1 year of follow-up.

As an additional related calculation, the 3-year failure rate will be determined as:

$$3\text{-year rate} = 1 - (1 - r)^{36}$$

- For example, if there are 0 failures in $200 \times 12 = 2,400$ women-months, the posterior distribution of the monthly failure rate is $\text{beta}(0.5, 0.5 + 2400)$. The upper Bayesian credible interval is (in Excel) $\text{betainv}(.975, 0.5, 0.5 + 2400) = 0.00105$. The upper 95% credible interval for the 1-year rate is $1 - (1 - 0.00105)^{12} = 0.0125$ or 1.25%. This value meets the pre-determined study success threshold of 2.1% for the 1-year rate. 2.1% refers to the Upper Confidence Limit of the Adiana 1-year failure rate and 2.8% refers to the Upper Confidence Limit of the Adiana 3-year failure rate. (from Table 5: Contraceptive Failure Rates, Adiana Permanent Contraception Instructions For Use, AW-03216-001 Rev. 003);

The analysis population is the Primary Effectiveness Cohort.

The primary objective of the PAS is to evaluate the contraceptive failure rate of Essure when NovaSure EA is performed following a successful Essure Confirmation Test and to demonstrate that the failure rate is reasonably low (see details below). Consistent with prior Essure clinical studies, a Bayesian approach will be used. The study will be considered a success if the posterior probability (PPr) that the observed failure rate at 1 year (rate1y) is $< 2.1\%$ is at least 97.5%, i.e.:

$$\text{PPr}(\text{rate1y} < 0.021) > 0.975 *$$

* i.e., a Type 1 error rate of 5%

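### Woman-months are counted by study participation, so months after conception-ending surgery and months with unknown pregnancy status can enter the primary denominator as event-free

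*SAP*

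**What the plan says.** The endpoint in SAP 3.1 is confirmed pregnancy "among subjects relying on Essure micro-inserts for permanent birth control when NovaSure is performed following a successful Essure Confirmation Test". SAP 6.2.1 and Protocol 8.4.1 treat each woman-month of follow-up as one Bernoulli trial of the device, and then fix the count: "A woman contributes as many women-months as her participation in the post-approval study". On timing they add: "The 1-year rate will be calculated when all participating women have reached at least 1 year of follow-up". The Primary Effectiveness Cohort (SAP 5) requires consent and transcervical insertion of the NovaSure device. It carries no at-risk condition. The supportive Kaplan-Meier analysis has no censoring rule.

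Four provisions bear on when participation ends or pregnancy status is known:

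- **Termination at discretion.** Protocol 5.2.1: "Subjects may be terminated from the study by the Investigator". The listed reasons include not retaining the device, with salpingectomy and other utero-tubal surgery among the examples.
- **Termination after insert loss.** Protocol 7.1.2.5, on expulsion or removal of a micro-insert: "subject will be followed for the duration of the adverse event, then terminated from the study". The same section asks women to report "any surgery which may remove some or all of her reproductive organs (i.e. hysterectomy, salpingectomy or oophorectomy"), and Protocol 7.1.2.4 raises such surgery at each yearly call. Neither section links the answer to w.
- **Lost subjects.** Protocol 5.2.1: "if a subject who is lost to follow-up is re-contacted, the subject will not be considered to have withdrawn from the study".
- **Pregnancy inquiry.** Protocol 7.1.2.4 describes the yearly call as covering current pregnancy and the preceding year. Between calls, Protocol 7.1.2.5 relies on self-report: "The subject will also be instructed to contact the Investigator immediately if, at any time during the study, subject thinks she might be pregnant".

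**The concern.** Two kinds of month are inside participation but are not informative trials of the device.

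1. **Months after surgery that makes conception impossible.** The gap is mainly surgery that leaves the inserts in place, or surgery not followed by termination. To this is added the time until an adverse event ends, where termination waits for it.
2. **Months with unobtained status.** A woman who misses the Year-2 call and is reached at Year 3 was never withdrawn. The Year-3 question as described looks back one year, so about 12 of her 36 months are unqueried but counted.

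Event-free months that carry no risk, or no information, enlarge w without the possibility of enlarging the pregnancy count f. For a given f, the posterior then shifts down and the upper limit shrinks, towards success. A pregnancy missed in an unqueried gap would also lower f; the figures below do not include that.

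**Working it through.** **Inputs.** Prior beta(0.5, 0.5); 1-year threshold 2.1% and 3-year threshold 2.8%; posterior probability 97.5% (all SAP 6.2.1). The Protocol 8.6 value of 95% is used only as a variant. n = 200 is the power basis and 220 the minimum enrolment. The share of affected months is not in the documents; up to 25% is assumed.

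**Formula.** Upper limit = 1 − (1 − r)^m, where r is the q-quantile of beta(0.5 + f, 0.5 + w − f), with m = 12 or 36.

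**Reproducing the plan.** f = 0, w = 200 × 12 = 2,400, q = 0.975: r = 0.001046 and the 1-year limit is 1.248%. The plan states 0.00105 and 1.25%. With beta(0.5, 600.5) as the yearly rate, the chance of 0 pregnancies among 200 women is 0.866, against the plan's simulated 0.861. The plan's figures hold; the question is only what belongs in w.

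**SAP 1-year rule (97.5%, limit 2.1%)**

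| f | w | Upper limit | Result |
|---|---|---|---|
| 0 | 2,400 | 1.25% | pass |
| 0 | 2,160 (10% removed) | 1.39% | pass |
| 0 | 1,800 (25% removed) | 1.66% | pass |
| 1 | 2,400 | 2.31% | fail |
| 1 | 2,640 (220 × 12) | 2.102% | fail |

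With 0 pregnancies the smallest passing w is 1,421, so (2,400 − 1,421)/2,400 = 41% would have to go. With 1 pregnancy 2,644 months are needed, and the rule fails before any removal.

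**SAP 3-year rule (97.5%, limit 2.8%)**

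| f | w | Upper limit | Result |
|---|---|---|---|
| 0 | 7,200 (200 × 36) | 1.25% | pass |
| 1 | 7,200 | 2.31% | pass |
| 1 | 6,480 (10% removed) | 2.56% | pass |
| 1 | 5,760 (20% removed) | 2.88% | fail |
| 2 | 7,200 | 3.16% | fail |

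With 1 pregnancy the smallest passing w is 5,926. From 7,200 that is (7,200 − 5,926)/7,200 = 17.7% removed; from 220 × 36 = 7,920 it is (7,920 − 5,926)/7,920 = 25.2%. With 0 pregnancies 3,184 months suffice.

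**Other boundaries**

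- *Protocol 95% rule, 1-year, 1 pregnancy:* 1.93% at 2,400 months. It fails below 2,210, that is, when more than (2,400 − 2,210)/2,400 = 7.9% is removed. This case exists only because Protocol 8.6 and the SAP state different probabilities. The Protocol's own table uses the two-sided limit, 0.023, at which 1 pregnancy already fails.
- *All follow-up pooled into the 1-year rate, 97.5%:* 6 pregnancies in 7,200 months pass at 2.04% and fail below 6,996 (2.8% removed). 5 pass at 1.81% and fail below 6,200 (13.9% removed). Under the plan's own prior, 5 or 6 pregnancies in 600 woman-years have a chance of about 0.8%.

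**The case against.** **Wording.** The sentence before the participation rule speaks of follow-up as a trial of the device, so a sympathetic reader could exclude months that test nothing. Reliance can also be read as an entry condition. Both readings are possible, but the only operative rule given for w is participation, and a programmer following it would count these months.

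**Surgery.** A reader might infer that the plan never stops follow-up after surgery. The documents do not support that. The inserts lie in the tubes, so surgery that takes out an insert may already fall under the removal provision of Protocol 7.1.2.5, and 5.2.1 names utero-tubal surgery as a possible reason for termination. The surgery part is therefore narrow, though not closed.

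**Gaps.** The exact wording of the call form is not available, because the case report form is not attached to this version (Protocol 14); it may ask about all time since the last contact. Sites hold several contact routes (Protocol 7.1.2.1), missed assessments are chased (SAP 4.3), and women are told to report a suspected pregnancy. These steps reduce the gap but do not say how its months enter w.

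**Realism.** A reader might take the 3-year reversal as a likely outcome. Exactly 1 pregnancy in 600 woman-years is not improbable under the plan's prior (about 18%), but the loss required is large: 7,200 − 5,926 = 1,274 months. From skipped calls alone that is 1,274/12, about 106 bridged gaps out of 400 Year-1 and Year-2 calls among 200 women. From surgery at month 18 alone it is 1,274/18, about 71 women not terminated. Dropout would thin the margin: if recorded w were 6,300 (an assumption), (6,300 − 5,926)/6,300 = 5.9% would suffice. Nothing in the documents shows such shares will occur.

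**Declared success.** The success statement in SAP 6.2.1 is the 1-year criterion; the 3-year rate is introduced as an additional calculation, though with its own threshold. At 2,400 months the SAP 1-year decision is the same with or without the correction, for 0 and for 1 pregnancy. This objection stands.

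**Direction.** A reader might extend the bias to all months after insert loss. That does not follow: such a woman may conceive, and Protocol 7.4.3 counts any pregnancy during the study as a device failure.

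**Conclusion.** The concern holds in a limited form. The rule for w does not match the endpoint, and for a given pregnancy count the mismatch can act only towards success. The shift is modest: 1.25% to 1.39% or 1.66% for the 1-year limit with 0 pregnancies, at assumed shares of 10% and 25%, without a change of decision. A decision changes only near a boundary. The plainest case is the 3-year test with 1 pregnancy, once more than 17.7% of 7,200 months (25.2% of 7,920) are removed. These full-follow-up totals and the removed shares are assumptions. A claim that the 1-year SAP result is at risk at 2,400 months, or that the 3-year result will probably reverse, would go beyond the documents. The point is still worth settling, because it concerns the denominator of the primary estimate and the supportive Kaplan-Meier analysis has no rule that would correct it.

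**What to change.** - **Define w** in SAP 6.2.1 and Protocol 8.4.1 as months from the NovaSure procedure to the earliest of conception, surgery that makes conception impossible, end of participation, or last contact with known pregnancy status. Use the same end dates for Kaplan-Meier.
- **Close gaps at source.** Word the yearly pregnancy inquiry to cover the whole time since the last completed contact. Gap months then have known status at re-contact and stay in w.
- **Gaps that remain unknown.** In a sensitivity analysis, censor at the last contact before the gap for both w and pregnancies, so that numerator and denominator match. Dropping only the gap months while keeping every pregnancy would bias the rate upward and would require a delayed-entry rule for Kaplan-Meier.
- **Numerator.** Keep every pregnancy during the study in the primary count, as Protocol 7.4.3 requires, including one after insert loss.
- **Transparency.** Report the total-participation version as a sensitivity analysis.
- **Reconcile** the termination passages in Protocol 5.2.1 and 7.1.2.5.

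Cost: wording in both documents, the call script and programming, with no new visits. Extirpative surgery is already asked about yearly, but some surgery, conception and contact dates may have to be derived. The downside is fewer woman-months and a slightly less favourable upper limit.

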6.2.2 Secondary Endpoint Analyses

The secondary endpoint in the PAS is the incidence of adverse events when NovaSure EA is performed in the presence of Essure micro-inserts. There is no specific study hypothesis. Instead, the safety profile will be analyzed using summary statistics on the Safety Cohort as described in Section 6.3.

6.2.3 Other Endpoint Analyses

6.2.3.1 Summary of subject evaluations

The following evaluations will be summarized descriptively for the Primary Effectiveness Cohort for 1-week, 1-year, 2-years and 3-years of follow-up:

- Subject's rating of comfort of wearing the micro-insert
- Subject's rating of overall satisfaction with the micro-insert
- Subject's rating of overall satisfaction with the treatment plan of Essure permanent birth control and Essure Confirmation Test, followed by NovaSure Treatment

6.3 Safety

The safety variables to be investigated in this study include the following:

- Adverse Events
 - Adverse events related (an AE that is at least possibly related to the Essure or NovaSure device/procedure) to Essure and/or NovaSure
 - Adverse events of special interest
 - Most common AEs ($\geq 1\%$)
- Serious Adverse Events (SAE)

- Most common SAEs ($\geq 1\%$)
- Device events for Essure and/or NovaSure
 - Device events leading to AEs
 - Device events that resulted in SAEs
 - Device events that could lead to SAEs
- Device removals
 - Number of subjects with removals
 - Removal procedures – days from last insert procedure to removal procedure, removal intended, primary reason for intentional device removal, procedures performed at time of device removal, number of devices removed per procedure
 - Essure inserts removed – insert location, complete device removal, device removed intact

The safety profile will be analyzed using summary statistics on the Safety Cohort.

6.3.1 Adverse Events

All AEs will be coded using MedDRA.

Frequency tables showing an overall summary of the number of events (where possible) and the number of subjects with AEs by system organ class (SOC) and preferred term (PT) will be given for the following types of AEs:

- All AEs
- AEs (possibly, probably, definitely) related to:
 - Essure device
 - NovaSure device
 - NovaSure procedure
 - Pre-existing condition
- AEs by intensity (mild, moderate, severe)
- AEs by outcome

- AEs of special interest
 - Defined as follows (updated annually by Medical Experts):

AE of Special Interest	Description	AEDECOD (PT)	AELLT
Abnormal Uterine Bleeding	Set to Y if AEDECOD equal to any of values in Column C:	Dysfunctional uterine bleeding	
		Genital hemorrhage	
		Genital haemorrhage	
		Menometrorrhagia	
		Menorrhagia	
		Metrorrhagia	
		Polymenorrhoea	
		Uterine hemorrhage	
		Uterine haemorrhage	
		Vaginal hemorrhage	
		Vaginal haemorrhage	
		Amenorrhea	
		Amenorrhoea	
		Hypomenorrhea	
		Hypomenorrhoea	
		Oligomenorrhea	
		Oligomenorrhoea	
		Bleeding anovulatory	
		Menstrual disorder	
Menstruation delayed			
Menstruation irregular			
Lower Abdominal Pelvic and Back Pain	Set to Y if AEDECOD='Back pain' and AELLT='Low back pain', otherwise set to Y if AEDECOD equal to any of values below:	Back pain	Low back pain
		Abdominal pain	
		Abdominal pain lower	
		Abdominal tenderness	
		Abdominal discomfort	
		Incision site pain	
		Implant site pain	
		Medical device discomfort	
		Medical device pain	
		Medical device site discomfort	
		Medical device site pain	
		Suprapubic pain	
		Visceral pain	
		Post ablation tubal ligation syndrome	
		Pubic pain	

		Groin pain	
		Genito-pelvic pain/penetration disorder	
		Uterine cervical pain	
		Ovulation pain	
		Pelvic pain	
		Pelvic discomfort	
		Dyspareunia	
		Adnexa uteri pain	
		Uterine tenderness	
		Uterine pain	
		Uterine spasm	
		Dysmenorrhoea	
		Menstrual discomfort	
		Premenstrual cramps	
Perforation	Set to Y if AEDECOD equal to any of values in Column C:	Fallopian tube perforation	
		Uterine perforation	
Upper genital tract infections	Set to Y if AEDECOD equal to any of values in Column C:	Endometritis	
		Salpingitis	
		Salpingo-oophritis	
		Pelvic inflammatory disease	
Expulsion or migration or unintentional removal of Essure inserts	Set to Y if AEDECOD equal to any of values in Column C:	Device dislocation	
		Device expulsion	
		Unintentional medical device removal	
Potential allergy/hypersensitivity to Essure inserts	Set to Y if AEDECOD equal to any of values in Column C:	Allergy to animals	
		Allergy to chemicals	
		Allergy to metals	
		Hypersensitivity	
		Multiple allergies	
		Pruritus	
		Rash	
		Rash pruritic	
		Seasonal allergy	
		Urticaria	
Auto-immune	Set to Y if AEDECOD equal to any of values in Column C:	Autoimmune disorder	
		Autoimmune thyroiditis	
		Multiple sclerosis	
		Multiple sclerosis relapse	
		Rheumatoid arthritis	

- AEs occurring in at least 1% of subjects

The same AE tables listed above will be repeated for treatment-emergent serious AEs, except for AEs of special interest.

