4.1 General Principles

The statistical evaluation will be performed by using the software package SAS release 9.2 or higher (SAS Institute Inc., Cary, NC, USA) or R release 3.0.2 or higher (R Foundation for Statistical Computing, Vienna, Austria). Baseline NovaSure EA and follow-up data will be summarized using the appropriate statistical method; continuous variables will be summarized using means, standard deviations, medians and quartiles. Categorical data will be summarized using frequency rates (e.g., count/sample size).

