4.6 Validity Review

Assignment of subjects to the analysis set described in Section 5 will be discussed and documented. In addition, protocol deviations will be discussed, reviewed, and categorized. Any changes to the statistical analysis prompted by the results of this meeting will be documented in an amendment and, if applicable, in a supplement to this SAP.

5. Analysis Sets

Primary effectiveness cohort

All subjects who sign a study-specific ICF and undergo insertion of the NovaSure device transcervically

Primary safety cohort

All subjects who sign a study-specific ICF and in whom a NovaSure procedure is attempted (e.g., subject who comes to the study site with the intent of having the procedure performed).

Enrolled cohort

The enrolled cohort includes any subject who signs the study-specific ICF.

6. Statistical Methodology

Variables measured on metrical scales will be summarized by use of descriptive statistics (number of subjects with non-missing observations, mean, standard deviation, minimum, 1st quartile, median, 3rd quartile, and maximum). Variables measured on ordinal or nominal scales will be summarized by use of frequency tables showing the number and percentage of subjects falling within a particular category.

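### Adverse event percentages in SAP 6.3.1 keep women who leave early in the denominator, so they understate cumulative incidence for later-onset events

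*SAP*

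**What the plan says.** SAP 6.2.2 states: "The secondary endpoint in the PAS is the incidence of adverse events when NovaSure EA is performed in the presence of Essure micro-inserts". It adds that "There is no specific study hypothesis" and refers to SAP 6.3, where "The safety profile will be analyzed using summary statistics on the Safety Cohort".

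The summary measure in SAP 6.3.1 is "Frequency tables showing an overall summary of the number of events (where possible) and the number of subjects with AEs by system organ class" and preferred term. That section gives neither a denominator nor a time window. Both have to be assembled from elsewhere:

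- SAP 4.1: "Categorical data will be summarized using frequency rates (e.g., count/sample size").
- SAP Section 6, opening paragraph: "frequency tables showing the number and percentage of subjects falling within a particular category".
- SAP Section 5, safety cohort: "All subjects who sign a study-specific ICF and in whom a NovaSure procedure is attempted".
- SAP 4.2: dropouts are analysed in every set for which they qualify and are not replaced.
- Protocol 7.4.1.3: AEs are collected from consent until the end of each woman's own participation, which is planned to last three years after NovaSure.
- Protocol 5.2.1 lists reasons for early exit, including loss to follow-up, an AE, death, and failure to retain the device. Under Protocol 7.1.2.5, after an insert expulsion or removal the "subject will be followed for the duration of the adverse event, then terminated from the study".

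Pregnancy is handled differently. SAP 6.2.1 uses woman-months of participation and adds a supportive Kaplan-Meier estimate.

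**The concern.** A woman who leaves at month 10 counts as one full unit in the denominator, yet an AE she has at month 20 cannot be counted. The ratio is then a mixture of risk and length of observation. It equals the risk over the whole follow-up only if nobody leaves early, or if the events happen before anyone leaves. The gap grows with later onset and with heavier loss.

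What is at stake is how the safety tables are read. A reader will take a percentage in a three-year study as the share of women expected to have that event in the period. For late events, such as pelvic pain or recurrent bleeding, that reading is too low. The SAP's table of AEs occurring in at least 1% of subjects applies its cut-off to the same proportion, so an uncommon late event can drop out of that table while remaining in the full one.

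A related gap is that the general AE tables are not split by onset. AE collection begins at consent, up to 30 days before NovaSure by the schedule in Protocol 7.1.1. SAP 6.3.1 mentions treatment emergence only for serious AEs. Events before the procedure, around it and up to three years later share one line, although the second study objective concerns AEs associated with performing NovaSure.

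**Working it through.** **Figures to reproduce.** The documents state no AE incidence, AE precision or dropout rate. The one power figure, 86% for the 1-year pregnancy rate, does not enter this calculation.

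**Inputs.**
- Follow-up T = 3 years (SAP Section 3).
- True 3-year incidence p = 10%: assumed, for illustration.
- 3-year loss D: not stated. SAP Section 3 enrols at least 220 and SAP 6.2.1 powers on 200, and 1 − 200/220 = 9.1%. The documents do not call the difference a dropout allowance, so 9.1% is an assumption. I show 5% to 40%.
- Loss is exponential and unrelated to AE risk: assumed.

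**Formula.** With loss hazard d = −ln(1 − D)/3, and events arising only between t0 and t1 at hazard h = −ln(1 − p)/(t1 − t0), the expected crude proportion is

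exp(−d·t0) × h/(h + d) × [1 − exp(−(h + d)(t1 − t0))].

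**One case in full (D = 9.1%, constant hazard over 0 to 3 years).** h = 0.03512 and d = 0.03177, so h/(h + d) = 0.525 and 1 − exp(−3 × 0.06689) = 0.182. The product is 0.0955, that is 9.5% against a true 10%.

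**Crude percentage when the true value is 10%:**

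| Onset of events | D = 5% | 9.1% | 20% | 30% | 40% |
|---|---|---|---|---|---|
| First week | 10.0 | 10.0 | 10.0 | 10.0 | 10.0 |
| Constant, years 0–3 | 9.8 | 9.5 | 9.0 | 8.4 | 7.9 |
| Years 2–3 only | 9.7 | 9.4 | 8.6 | 7.9 | 7.2 |
| Year 3 only | 9.6 | 9.2 | 8.3 | 7.4 | 6.6 |

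For year-3 events the relative shortfall is about 4%, 8%, 17%, 26% and 34% across the columns.

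**How far 9.1% can be trusted.** The n=200 belongs to a 1-year calculation. If the 20 extra women were meant to cover one year's loss, the same yearly loss would compound to 1 − (200/220)³ = 24.9% over three years, and the constant-hazard figure would be 8.7%. This too is an assumption.

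**Scale against sampling error.** For 10% of 220 women the 95% half-width is 1.96 × √(0.1 × 0.9/220) = 4.0 points. The shift at 9.1% loss is 0.5 points (constant hazard) to 0.8 points (year-3 onset). At 40% loss it is 2.1 to 3.4 points. The shift always goes the same way and does not shrink with sample size.

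**The case against.** **The endpoint is not defined as a three-year incidence.** That is correct. The documents call it AE data, or the incidence of AEs when NovaSure is performed. For peri-procedural events, which are closest to the second objective, the crude percentage is sound at every level of loss in the table. A reader might infer that the plan systematically under-reports AEs. It does not: every observed event is counted, including one that leads to exit. Only the percentage, read as a risk over the full follow-up, is low.

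**Timing and attribution are partly covered.** A reader might also infer that the tables cannot show what clusters around NovaSure. That goes too far. SAP 6.3.1 tabulates AEs by relation to the NovaSure procedure, the NovaSure device and the Essure device. SAP 6.1 summarises expulsion at 1 week and 1, 2 and 3 years, and SAP 6.3 gives days to removal. Two limits remain. Days to removal run from the last insert procedure, not from NovaSure. And the temporal factor offered to investigators in Protocol 7.4.1.2.3 is sequence from Essure placement, which every study AE satisfies because confirmed placement is an entry condition.

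**The effect may be small.** At 9% loss it is well inside sampling error. Protocol 7.1.2.1 asks sites for contact details of at least two relatives and two acquaintances, and SAP 6.1 reports disposition, reasons for termination and visit accountability. This stands as to size. But disposition is not linked to the AE rates, so a reader cannot correct the percentages from it.

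**A simple remedy could add bias.** This stands and shapes the fix. Kaplan-Meier with censoring at insert removal or utero-tubal surgery would overstate device-related incidence, because those exits are competing events. SAP Table 1 moves completely missing start dates to the NovaSure date, and does the same for partial dates that match the procedure year or month. A plain onset split would pile those AEs on Day 0.

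**Conclusion.** The point holds in a limited form. The planned percentages understate cumulative incidence for later-onset AEs whenever women leave early, and no planned AE output uses time at risk. First-week events are essentially unaffected.

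The size cannot be fixed from the documents. For a true 10% it is 0.5 to 0.8 points at an assumed 9% loss, and 1.0 to 3.4 points at an assumed 20 to 40% loss. These figures assume loss unrelated to AE risk. Nothing in the text supports a claim that loss will be heavy or the understatement large.

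The endpoint is descriptive, so no type I error, power or success criterion is touched. The change is still worth making: the SAP already uses person-time for pregnancy, and its date-imputation rules presuppose the AE dates that the added tables need.

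**What to change.** In SAP 6.3.1, keep the crude tables and add the following for all AEs, related AEs, SAEs and each special-interest category:

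1. Events, and first events, per 100 woman-years.
2. Cumulative incidence at 1 and 3 years with 95% CI and numbers at risk, censoring at loss or withdrawal. For device-related and uterine AEs, treat death, insert removal or expulsion, and extirpative surgery as competing events (Aalen-Johansen). Count any AE that itself causes the exit. For other AEs, state which exits censor.
3. Counts by onset period: before the procedure, Day 0–9 (the one-week visit plus its two-day window), and later. Show AEs whose start date was imputed to the procedure date on a separate line, so that they do not create false clustering at Day 0.

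State the denominator and the time window in 6.3.1 itself. A single woman-year rate averages an early peak with a long tail, so item 1 should be read with item 3.

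The cost is SAP wording and a few tables from data already held. Reported incidences of later events will be slightly higher.
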